## 1. Version History

Version	Summary of Changes	Author(s)/Title
1.0	

'Not Applicable, New Document'

	[name]/ Sr Statistician [name]/ Sr Pr Test Engineering

## 2. List of Abbreviations and Definitions of Terms

Abbreviation	Definition
ACC	American College of Cardiology
AHA	American Heart Association
BMI	Body Mass Index
CABG	Coronary Artery Bypass Graft
CIP	Clinical Investigation Plan
CEC	Clinical Events Committee
CRF	Case Report Form
CRT	Cardiac Resynchronization Therapy: Established pacing therapy for patients with heart failure
CRT-D	Cardiac Resynchronization Therapy - Defibrillator
CRT-P	Cardiac Resynchronization Therapy - Pacemaker
CS cannulation	Coronary Sinus cannulation
eCRF	Electronic Case Report Form
EMEA	Europe, Middle East, Africa
FDA	Food and Drug Administration
HRS	Heart Rhythm Society
IDE	Investigational Device Exemption
LV	Left Ventricular
MI	Myocardial Infarction
NYHA	New York Heart Association
OUS	Outside of the United States
PCT	Pacing Capture Threshold
PMA	Premarket Approval
PNS	Phrenic Nerve Stimulation

Abbreviation	Definition
PTCA	Percutaneous Transluminal Coronary Angioplasty
RA	Right Atrial
RV	Right Ventricular
SAP	Statistical Analysis Plan
US	United States

### 3. Introduction

The Attain Stability™ Quad LV Lead Clinical Study is a prospective, non-randomized, multi-site, global, Investigational Device Exemption (IDE), interventional clinical study. The purpose of this clinical study is to evaluate the safety and efficacy of the Attain Stability Quad MRI SureScan LV Lead (Model 4798). This study will not be considered investigational in geographies with CE Mark of the Attain Stability Quad MRI SureScan LV lead (Model 4798). However, data collected from all study subjects will be represented in the PMA Supplement (PMA-S) and all clinical reports. Subjects successfully implanted with the Attain Stability Quad MRI SureScan LV Lead (Model 4798) will be followed at implant, three months, six months and every six months thereafter until FDA approval is obtained or until study closure, whichever comes first.

This Statistical Analysis Plan (SAP) has been designed to document, before data is analyzed, the rationale for the study design, and the planned analyses related to the primary objective and secondary objectives. Additional analysis of the study data beyond this plan may be conducted to provide evidence further supporting the market approval of the lead and additional publications. The statistical analyses conducted for publications and/or ad-hoc requests may not be limited to this document.

The Attain Stability™ Quad Clinical Study CIP Version 3.0, dated 20 March 2017 was used to create this SAP.

### 4. Study Objectives

#### 4.1. Primary objective

The primary objective of the study is to assess the safety and characterize the efficacy of the Attain Stability Quad MRI SureScan LV Lead (Model 4798).

#### **Primary Safety Objective: Lead complication-free rate at 6 months**

The Attain Stability Quad MRI SureScan LV Lead (Model 4798) will be considered safe if the probability of subjects free of Model 4798 lead-related complications at 6 months post-implant is greater than 87%.

#### **Primary Efficacy Objectives: Lead pacing capture thresholds at 6 months**

To demonstrate the effectiveness of the Attain Stability Quad MRI SureScan LV Lead (Model 4798), the study will evaluate the likelihood that there are at least two programmable vectors for each patient post

implant. The effectiveness of this lead will be evaluated based on two primary efficacy objectives. More specifically, both primary efficacy objectives must be met simultaneously.

#### **Primary Efficacy Objective #1**

The Attain Stability Quad MRI SureScan LV Lead (Model 4798) will meet this objective if the proportion of subjects with at least one LV lead pacing vector having a pacing capture threshold less than or equal to 2.5 V at 0.5 ms pulse width (with absence of Phrenic Nerve Stimulation (PNS) at 5.0 V) at 6 months post-implant is greater than 80%.

#### **Primary Efficacy Objective #2**

The Attain Stability Quad MRI SureScan LV Lead (Model 4798) will meet this objective if the proportion of subjects with at least one additional (or second) LV lead pacing vector having a pacing capture threshold less than or equal to 4.0 V at 0.5 ms pulse width (with absence of PNS at 5.0 V) at 6 months post-implant is greater than 80%.

## **4.2. Secondary Objectives**

The secondary objectives are descriptive in nature and are intended to provide additional information about the Attain Stability Quad MRI SureScan LV Lead (Model 4798). There will be no established performance requirements for these secondary objectives.

- To summarize implant procedure related information: success rate, implant related times
- To estimate 6-month reliability: post implant lead failure modes (i.e. complication rate)
- To estimate electrical measurement values (Pacing Capture Thresholds (PCTs) and Lead Impedance) at 6 months post-implant

## **5. Investigation Plan**

The Attain Stability™ Quad Clinical Study is a prospective, non-randomized, multi-site, global, IDE, interventional clinical study. Up to 471 subjects may be enrolled in the study.

The inclusion and exclusion criteria to be enrolled in the study are as follows:

#### **Inclusion criteria**

- Patient meets CRT implant criteria as determined by local regulatory and/or hospital policy (i.e. US subjects should meet CRT device indications per the HRS/ACC/AHA guidelines)
- Patient (or legally authorized representative) has signed and dated the study-specific Consent Form
- Patient is 18 years of age or older, or is of legal age to give informed consent per local and national law
- Patient is expected to remain available for follow-up visits

#### **Exclusion criteria**

- Patient has had a previous unsuccessful LV lead implant attempt
- Patient has a previous CRT system or LV lead implanted (for example, transvenous or epicardial)
- Patient is currently implanted with a recalled (i.e. market-withdrawn, recalled or safety alert) RA and/or RV lead
- Patient has known coronary venous vasculature that is inadequate for lead placement
- Patient has unstable angina pectoris or has had an acute myocardial infarction (MI) within the past 30 days
- Patient has had a coronary artery bypass graft (CABG) or percutaneous transluminal coronary angioplasty (PTCA) within the past 90 days

- Patient has contraindications for standard transvenous cardiac pacing (e.g., mechanical right heart valve)
- Patient has had a heart transplant (patients waiting for heart transplants are allowed in the study)
- Patient has known renal insufficiency and/or significant allergy to contrast dye that would prevent them from receiving an occlusive venogram during the implant procedure
- Patient is contraindicated for <1mg dexamethasone acetate
- Patient is enrolled in any concurrent drug and/or device study that may confound the results of this study
- Patient has a terminal illness and is not expected to survive more than six months
- Patient meets exclusion criteria required by local law (e.g. age, pregnancy, breast feeding, etc.)
- Patient is unable to tolerate an urgent thoracotomy

Selection of subjects, treatment of subjects, and evaluation of study data are potential sources of bias. Methods incorporated in the study design to minimize potential bias include (but are not limited to):

- Subjects will be evaluated at baseline to confirm eligibility for enrollment with defined inclusion/exclusion criteria
- Subject demographics and medical history will be collected at baseline and differences that may affect primary endpoints will be identified
- To ensure widespread distribution of data between sites, the maximum number of subjects allowed per site is 50
- All implanters in the study will be experienced in the implant of CRT-P and/or CRT-D systems
- Data collection requirements and study procedures will be standardized across all sites and geographies
- All study site personnel and Medtronic personnel will be trained on their respective aspects of the study using standardized training materials, and required to follow the CIP
- Per the specifications in the Monitoring Plan, monitoring visits will be conducted for adherence to the CIP and to verify the CRF data against source data
- Pre-defined statistical methods specified in the CIP and the Statistical Analysis Plan (SAP) will be followed
- The Steering Committee members will not have influence on the treatment decisions by study site investigators during the trial
- An independent and blinded CEC will regularly review and adjudicate reported adverse events and deaths
- Registration of the trial on ClinicalTrials.gov and the publication plan will ensure that study results will be reported
- All study investigators are required to meet 21 CFR Part 54, Financial Disclosure by Clinical Investigators, to identify potential bias due to financial interest in the outcome of the study

## 6. Determination of Sample Size

The sample size requirement at 6-months for each of the study objectives is displayed in

Table 1. The first row does not account for attrition, while the second row is inflated by 15% attrition which accounts for 5% pre-procedure and 10% post procedure attritions. The sample size requirement for Secondary Objective #2 was given by the FDA as a requirement for evaluating post implant lead failures. Therefore, the overall sample size for the study is 471.

**Table 1: Require Sample size by Study Objective**

	Primary Safety Objective	Primary Efficacy Objective #1	Primary Efficacy Objective #2	Secondary Objective #1	Secondary Objective #2 (post-implant failure modes)	Secondary Objective #3	Overall
Number needed at 6-months	170	145	50	NA	400	NA	400
Number of enrollments	200	171	59	NA	471	NA	471

## 7. Statistical Methods

### 7.1. Study Subjects

#### 7.1.1. Disposition of Subjects

A STROBE flow diagram will be used to describe the disposition of study subjects.

Figure 1 shows an example of a blank STROBE flow diagram.

**Allocation:**

Since the Attain Stability™ Quad Clinical Study is not a randomized study, all study subjects that are enrolled are allocated to the intervention (i.e. implanted with Attain Stability™ Quad Clinical Study).

**Follow-up:**

[figure not shown]
All Model 4798 lead implanted subjects will be followed until study closure or subject exiting from the study due, but not limited, to the following reasons:

- Study subject withdrawal of consent
- Study subject death
- Lost to follow-up
- Investigator withdraws subject from the study
- Other reasons described by the study subject

**Analysis:**

Analyses of study objectives will be completed for subjects with valid data entries, e.g. save-complete case report forms and CEC fully adjudicated adverse events, etc. If there is missing data that prevents the analysis of a pre-specified objective then those test subjects will be excluded from that objective. Unless otherwise specified, there will be no imputation for missing data. Additional sensitivity analysis will be carried out to assess impact of missing data on study objectives.

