#### **Analysis Set #1:**

All subjects who undergo Model 4798 lead implant attempt procedure.

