### 7.3. Handling of Missing Data and Dropouts

Unless otherwise specified, if data is missing then there will be no imputation of the data. Instead, subjects with missing data will be excluded. Survival analyses will consider time to event censored at the last contact for lost to follow-up subjects.

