## 7.8. Evaluation of Objectives

### 7.8.1. Primary Safety Objective

The Attain Stability™ Quad MRI SureScan LV Lead (Model 4798) will be considered safe if the probability of subjects free of Model 4798 lead-related complications at 6 months post-implant is greater than 87% (i.e., the lower bound of a one-sided 97.5% confidence interval must be greater than 87%).

Hypothesis:

$H_0: S_{(6\text{-month})} \leq 87\%$

$H_1: S_{(6\text{-month})} > 87\%$

where  $S_{6\text{-month}}$  is the probability that a subject remains free from Model 4798 lead related complications through 6 months since implant.

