#### Analysis Method:

A standard time to first event survival analysis type will be performed to investigate the hypothesis proposed in the primary safety objective. More specifically, the Kaplan-Meier method will be used to estimate the probability of a subject surviving from any Model 4798 lead-related complication as a function of time; the 1-sided 97.5% confidence limit lower bound for the survival probability at 6 months (183 days) will be calculated using the log-log survival function approach (Kalbfleisch and Prentice 2002). For the purposes of this analysis, time 0 is defined as the day a subject undergoes the implant procedure of the Attain Stability Quad MRI SureScan LV Lead (Model 4798), which is independent of success status of this implant procedure. For the survival analysis, an event is defined as an Attain Stability Quad MRI SureScan LV Lead (Model 4798) related complication according to Clinical Events Committee (CEC) adjudication. Event date is the onset date of a subject's first complication that is related to the Attain Stability Quad MRI SureScan LV Lead (Model 4798). The definition of "complication" and "LV lead related" can be found on the study CIP. Subjects who undergo an Attain Stability Quad MRI SureScan LV Lead (Model 4798) implant attempt and do not experience any LV lead related complications will have their time to event censored at their last known time to exposure to the initial Attain Stability Quad MRI SureScan LV Lead (Model 4798). For any lost to follow-up subject, the last contact date will be used as the censor date.

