#### Additional Analysis:

Sensitivity analyses will be performed to assess the robustness of the results. In particular,

---

 Kalbfleisch, J.D. and Prentice, R.L. (2002). *The Statistical Analysis of Failure Time Data*. Second Edition. John Wiley & Sons, Inc. New York.

- In the event a site investigator disagrees with the CEC's classification of an event, site investigator's event classification will be disclosed, however only CEC final adjudication results will be used for the statistical analysis. In the event when CEC final adjudication of relatedness of an event is "unknown", the "worst-case" scenario analysis will be carried out where the event will be counted as a lead related event in addition to the primary analysis of this objective.
- A tipping point survival analysis will be performed. In particular, subjects having time to event censored before 6 months will be considered one-by-one (by implant date) as observed events. Therefore, the 6-month survival intervals will be calculated for all scenarios in which a censored subject becomes an event.
- A similar survival analysis will be performed, but considering the first 200 subjects who had at least an implant attempt of the Attain Stability Quad MRI SureScan LV Lead - Model 4798. The first 200 subjects will be selected based on the date of implant. In case of a tie (for the 200th position) among subjects who are implanted on the same day, the initial procedure time (converted to U.S. central time) will be used to select the first 200 subjects.

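### The rule limiting analyses to subjects with fully adjudicated events conflicts with the safety analysis set and, if any adjudication is pending, can raise the complication-free rate

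*SAP*

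**What the plan says.** Section 7.1.1 (Disposition of Subjects, Analysis) says that objectives are analysed for "subjects with valid data entries, e.g. save-complete case report forms and CEC fully adjudicated adverse events". It continues: "If there is missing data that prevents the analysis of a pre-specified objective then those test subjects will be excluded from that objective". There is no imputation unless otherwise specified. The paragraph ends with a promise: "Additional sensitivity analysis will be carried out to assess impact of missing data on study objectives". No method is given for it. Section 7.3 repeats that "subjects with missing data will be excluded".

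Section 7.1.3 defines Analysis Set #1 as "All subjects who undergo Model 4798 lead implant attempt procedure", and section 7.8.1 assigns that set to the primary safety objective. Neither place makes membership depend on adjudication.

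In section 7.8.1 an event is a lead-related complication as adjudicated by the CEC, and only the CEC's final result counts. The success criterion is that "the lower bound of a one-sided 97.5% confidence interval must be greater than 87" per cent, using a Kaplan-Meier estimate at day 183 with a log-log limit. Two of the sensitivity analyses bear on this point:
- When the CEC's final result on relatedness is unknown, a worst-case "scenario analysis will be carried out where the event will be counted as a lead related event".
- A tipping-point analysis turns subjects censored before 6 months into events, one at a time.

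**The concern.** The two definitions of who enters the primary safety analysis differ. Section 7.1.1 sets a condition on the subject and applies it to study objectives in general. Analysis Set #1 has no such condition.

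The condition is also tied to the outcome. Only a subject with a reported event can have one awaiting adjudication, so an event-free subject can never be removed on this ground. If open events turn out to be lead-related more often than the event rate among the subjects kept, removal shifts the estimate towards declaring the lead safe.

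The stated safeguards do not cover this case. The worst-case analysis starts from a final CEC result, and a pending event has none. The tipping-point analysis works on censored subjects, and an excluded subject is not censored. The missing-data sensitivity analysis in section 7.1.1 has no stated method, so it cannot be counted on to cover it.

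**Working it through.** **Inputs.** From the SAP: bound 87%, one-sided 97.5% limit, log-log method, day 183 (section 7.8.1); 170 subjects needed at 6 months for safety and 400 overall, with 15% attrition made up of 5% before and 10% after the procedure (section 6, Table 1). Assumed, because the SAP gives no figure: the numbers of confirmed and pending events, and complete follow-up to day 183.

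**Plan's own figures.** 170 / 0.85 = 200 and 400 / 0.85 = 470.6, rounded up to 471. Both match Table 1. Attempts expected from 471 enrolments: 471 × 0.95 = 447.45, taken as 447.

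**Lower limit.** With f events in n subjects and no censoring, S = 1 − f/n, se = √(S(1 − S)/n) / (S·|ln S|), and the lower limit is S^exp(1.96·se).

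| Events / subjects | S | se | Lower limit | Against 87% |
|---|---|---|---|---|
| 43 / 447 | 0.9038 | 0.1526 | 87.25% | pass |
| 46 / 447 | 0.8971 | 0.1475 | 86.50% | fail |
| 43 / 444 | 0.9032 | 0.1526 | 87.17% | pass |

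The last two rows are the same trial with 46 true events, first with all counted and then with 3 pending subjects excluded. The first row shows the looser reading, in which the 3 subjects stay in but their events do not count because no final CEC result exists. That also passes.

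**Direction and size of the bias.** Let k of N subjects be excluded, q be their true lead-complication rate and r the rate among those kept. The true event rate minus the reported one is (k/N)(q − r). In the example, (3/447) × (1 − 0.0968) = 0.006, or 0.6 percentage points. The bias is zero when k = 0 and negative when q < r: with 400 subjects, 20 events and 10 pending that all prove unrelated, exclusion gives 20/390, or 94.87% complication-free, against 95.00%.

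**Where the verdict can change.** At n = 447 and all pending events lead-related, it flips with 41–43 confirmed events if 3 are pending, 39–43 if 5, and 34–42 if 10. Away from the bound it does not: at n = 400 with 20 confirmed and 5 pending, exclusion gives 94.9% (limit 92.3%) and counting all as events gives 93.75% (limit 90.9%). Both pass.

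**False-pass probability at a true rate of exactly 87%** (simulation, n = 447): 1.7% with nothing pending, 4.2% if 5% of the lead-related events are pending and excluded, and 9.2% if 10% are. If, in addition, 20% of event-free subjects have an unrelated event under review with the same pending share, the last two become 3.9% and 7.0%.

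**The case against.** The best counter-argument is that section 7.1.1 describes the analysis box of the flow diagram and lists, by way of example, what makes data ready to analyse. Read literally, it would drop a subject for any open event, even one arising after month 6, which is unlikely to be intended. Section 7.8.1 then names Analysis Set #1 and sorts its subjects into events and censored observations, with no excluded category. Section 5 says that the CEC reviews events regularly, and the endpoint closes at day 183, so continued follow-up does not show that 6-month events stay open. Data-lock rules may sit in the protocol or a CEC charter.

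Much of this stands. The data-readiness reading is possible, and nothing shows that any event will be pending. A reader might infer that the primary safety result is certain to be biased upwards. The SAP does not support that: it gives no count of pending events, and since all system- and procedure-related events go to the committee, some open ones may prove unrelated.

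The size argument also stands. The SAP gives no assumed rate for its 170 subjects, but with at most 13 failures allowed the power is 0.86 at a 94% complication-free rate and 0.91 at 94.5%. If customary power was intended, about 6% events were expected. At n = 447 and a 6% rate, excluding 10% of events changes about 0.1% of verdicts; at 7%, about 1.2%.

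The objection does not remove the conflict. Section 7.1.1 words the condition per subject and prescribes exclusion, and nothing in the SAP requires adjudication to be complete before the analysis. Even on the data-readiness reading, the handling of a pending event is not stated.

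**Conclusion.** The point holds as a conflict in the SAP with a conditional consequence. Section 7.1.1 and Analysis Set #1 disagree on who enters the primary safety analysis, and the section 7.1.1 rule, taken literally, excludes on the outcome without a stated sensitivity analysis to expose it. An upward bias needs two conditions: adjudications pending at the data cut, and a higher lead-complication risk in those subjects than in the rest. The second is plausible, since they have a reported event. The verdict is at risk only near the 87% bound, and the illustrations rest on assumed counts, 447 attempts and no censoring. This should be corrected before analysis, but it does not show that the safety conclusion will be wrong.

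A reader might also infer that pending events should be classified by the investigator in the primary analysis. Section 7.8.1 rules that out, because only final CEC results are used.

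**What to change.** Amend sections 7.1.1, 7.3 and 7.8.1 of the SAP as follows:
- No Analysis Set #1 subject is left out of the safety Kaplan-Meier analysis because of incomplete forms or pending adjudication.
- CEC adjudication of all events with onset through day 183 is complete before the primary safety analysis is run.
- If any such event is still pending, the subject stays in the set, the event is counted as lead-related in the existing worst-case analysis, and the number pending is reported.
- Final CEC adjudication remains the only basis for the primary event definition.

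This is a wording change and needs no new data. The cost is a possible short wait for adjudication and, if anything is still open, a slightly less favourable worst-case rate. If adjudication would have been complete anyway, it costs nothing.

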**Figure 1 – Attain Stability™ Quad Clinical Study**

### 7.1.2. CIP Deviations

Deviations from the CIP will be collected on the Study Deviation CRF. Deviations will be summarized in the final report in a table by coded category. Deviation coding will be performed by Medtronic. The number of deviations per category, and the number and percentage of subjects with a deviation in each category will be reported.

